## 6. PATIENT ENROLLMENT

**Phase I Dose Escalation Portion** – Prior to discussing protocol entry with the patient, contact the City of Hope Data Coordinating Center to ensure that a treatment slot on the protocol is available.

### **Phase I and II Patient Enrollment**

The screening period for a particular patient commences when the patient signs the informed consent. Consent must be signed before any study-specific tests may be performed. After a patient has been screened and has successfully fulfilled all eligibility criteria, the site representative will email the inclusion/exclusion checklist and all other required source documentation to the City of Hope Data Coordinating Center. In order to ensure privacy/security, please ensure that you type #secure# in the subject line of all correspondence related to the trial/patient:

[name], CCRC  
Multiple Myeloma Project Manager  
[contact] [name]  
[contact]  
Email: [[contact]](mailto:[contact])

A unique patient number will be assigned at that time that will be used to identify the patient throughout the clinical study and must be used on all study documentation related to that patient. Patients will be assigned to a dose level at enrollment. Prior to accepting the registration, the COH DCC staff member will verify the following:

1. IRB approval at the registering institution
2. Patient eligibility
3. Existence of a signed consent form
4. Existence of a signed authorization for use and disclosure of protected health information (if applicable).

Treatment cannot begin prior to registration and must begin  $\leq$  7 days after registration. Pretreatment tests/procedures must be completed within the guidelines specified on the test schedule.

## 7. STUDY TREATMENT

### 7.1 Dose and Schedule

The phase I study will follow a standard 3 + 3 dose escalation design, to evaluate toxicities associated with MLN9708 when given in combination with pomalidomide and dexamethasone. Two doses of MLN9708 (3 mg and 4 mg) will be tested in up to three possible dose levels.

### 7.2 Dose Levels to be Tested

Schedule: Each cycle is 28 days			
Dose Level	Pomalidomide	MLN9708	Dexamethasone*
-1	3mg daily on days 1-21	3 mg on days 1, 8 and 15	40 mg on days 1, 8, 15 and 22
1	4 mg daily on days 1 - 21	3 mg on days 1, 8 and 15	40 mg on days 1, 8, 15 and 22
2	4 mg daily on days 1 - 21	4 mg on days 1, 8 and 15	40 mg on days 1, 8, 15 and 22

\*: Patients  $>75$  years, at the time of trial registration, will receive a Dexamethasone dose of 20 mg on the same set schedule.

### 7.3 Dose Limiting Toxicity/Unacceptable Toxicity

Dose Limiting Toxicity (DLT) is defined as any of the following toxicities that are at least possibly related to either Pomalidomide or MLN9708 that occur during cycle 1. Toxicity will be graded according to the NCI-Common Terminology Criteria for Adverse Events, Version 4.03.

Note: The Phase II portion of the study will use the same definition to define unacceptable toxicity.

For the purposes of this study, DLT will be defined as:

- Grade 4 neutropenia
- Grade 3 neutropenia with fevers  $\geq 38.5^{\circ}\text{C}$
- Grade 4 thrombocytopenia
- Grade 3 thrombocytopenia with bleeding
- Grade 3 or higher non-hematological toxicity will be considered dose limiting with the following exceptions: diarrhea, fatigue, nausea or vomiting will only be considered dose limiting if, after 48 hours it has not recovered to  $<\text{Grade 3}$  (despite maximal medical therapy), allergic reaction/hypersensitivity, or electrolyte/metabolic toxicity unable to be corrected to  $<\text{Grade 1}$  or baseline within 48 hours will be considered dose limiting.
- Delay in starting cycle 2 on the scheduled day 1 for  $> 7$  days due to treatment related toxicity
- Any dose modification or delay of MLN9708 or Pomalidomide during cycle 1, except modifications/delays done in response to hypo- hyperthyroidism  $\leq\text{Grade 2}$ , herpes zoster infection, all considered idiopathic or intrinsic to the underlying myeloma.

#### 7.4 Dose Escalation/Expansion

DLT incidence will be based on toxicity events encountered during the first cycle of treatment with the combination of MLN9708, pomalidomide and dexamethasone.

Dose de-escalation, escalation or cohort expansion will only take place after 3 patients are fully assessed using the Common Terminology Criteria for Adverse Events (CTCAE) of the National Cancer Institute (NCI) version 4.03 following the completion of cycle 1.

Dose escalation will occur according to the following rules:

- If zero out of 3 evaluable patients has a DLT in cycle 1 then the next dose level of combination therapy will be tested.
- If 1 out of 3 evaluable patients has a DLT in cycle 1, three additional patients will be assessed at the same dose level of combination therapy.
- If 2 out of 3 patients have a DLT in cycle 1, dose escalation will cease and the next lower dose level of combination therapy will be expanded. Note: If 2 of 3 experience DLT on dose level -1, the trial will be stopped.
- If 1 out of 6 evaluable patients has a DLT in cycle 1, then dose escalation to the next dose level of combination therapy will continue.

- If 2 or more out of 6 patients have a DLT in cycle 1, dose escalation will cease and the next lower dose level of combination therapy will be expanded. Note: If 2 of 6 experience DLT on dose level -1 the trial will be stopped.

The highest dose level that produces  $\leq 1/6$  DLTs in cycle 1 will be the maximum tolerated dose (MTD).

Note: Patients may continue therapy unless there is unacceptable toxicity, disease progression or withdrawal of consent.

### **7.5 Recommended Phase II Dose (RP2D)**

The MTD will be based on the assessment of DLT during cycle 1 (see section 7.4). The MTD will be defined as the highest dose at which  $\leq 1/6$  patients in a cohort experience DLT. The recommended phase II dose (RP2D) of MLN9708 and pomalidomide will generally be the MTD, but it may be less than the MTD based on a review of available data/cumulative toxicities from phase I.

### **7.6 Study Drug Administration**

All protocol-specific criteria for administration of study drug must be met and documented before drug administration. Study drug will be administered or dispensed only to eligible patients under the supervision of the investigator or identified subinvestigator(s). Patients should be monitored for toxicity, as necessary, and doses of study drug should be modified as needed to accommodate patient tolerance to treatment; this may include symptomatic treatment, dose interruptions, and adjustments of dose.

#### **7.6.1 MLN9708 Administration**

Patients should be instructed to swallow MLN9708 capsules whole, with water, and not to break, chew, or open the capsules. MLN9708 should be taken on an empty stomach (no food or drink) at least 1 hour before or 2 hours after a meal. Each capsule should be swallowed separately with a sip of water. A total of approximately 8 ounces (240 mL) of water should be taken with the capsules.

Missed doses can be taken as soon as the patient remembers if the next scheduled dose is 72 hours or more away. A double dose should not be taken to make up for a missed dose. If the patient vomits after taking a dose, the patient should not repeat the dose but should resume dosing at the time of the next scheduled dose.

### **7.6.2 Pomalidomide Administration**

Pomalidomide capsules should be swallowed whole, and should not be broken, chewed or opened. Pomalidomide should be taken without food, at least 2 hours before or 2 hours after a meal. Pomalidomide capsules may be taken with water.

If a dose of pomalidomide is missed, it should be taken as soon as possible on the same day. If it is missed for the entire day, it should not be made up, rather it should be taken at the next scheduled time point. Similarly, if the patient vomits after taking a dose, the patient should not repeat the dose but should resume dosing at the time of the next scheduled dose.

Patients who take more than the prescribed dose of pomalidomide should be instructed to seek emergency medical care if needed and contact study staff immediately.

Pomalidomide (POMALYST®) will be provided to research patients for the duration of their participation in this trial at no charge to them or their insurance providers. Pomalidomide will be provided in accordance with the Celgene Corporation's POMALYST REMSTM program. Per the standard POMALYST REMSTM program requirements, all physicians who prescribe pomalidomide for research patients enrolled into this trial, and all research patients enrolled into this trial, must be registered in and must comply with all requirements of the POMALYST REMSTM program.

Drug will be shipped on a per patient basis by the contract pharmacy to the clinic site for IND studies. Only enough pomalidomide for one cycle of therapy will be supplied to the patient each cycle. This is in accordance with the POMALYST REMSTM program.

#### Special Handling Instructions

Female caregivers of childbearing potential should not handle or administer pomalidomide unless they are wearing gloves.

### **7.6.3 Dexamethasone Administration**

Dexamethasone is commercially available and commercial supplies will be used for this study.

Oral dexamethasone will be given on an outpatient basis. Missed doses of dexamethasone will not be made up. Similarly, if the patient vomits after taking a dose, the patient should not repeat the dose but should resume dosing at the time of the next scheduled dose. Procedures for dose reductions and delays are summarized in Section 7.9.2.

#### 7.6.4 Growth Factor Administration

For the Phase I portion of the study, growth factors, granulocyte colony stimulating factor [G-CSF], may be given prophylactically for at least two days on days 21 – 26 during or beyond cycle 2. For the Phase II portion of the study, G-CSF may be given prophylactically for at least two days on days 21-26 during or beyond cycle 1. It will be administered subcutaneously at a dose of 5ug/kg or per institutional standard practice dosing either daily or every other day for a minimum of two doses. If patients experience neutropenia or dosing delays, we would recommend consideration of growth factor in subsequent cycles.

### 7.7 Dose Modification Guidelines

Patients will be evaluated for adverse events at each visit with the NCI Common Toxicity Criteria, Version 4.03 used as a guide for the grading of severity.

As defined in section 7.3, during the phase I portion of the study, any toxicity related dose modification or delay of MLN9708 or Pomalidomide during cycle 1 except modifications/delays done in response to hypo- hyperthyroidism <=Grade 2, herpes zoster infection, all considered idiopathic or intrinsic to the underlying myeloma is a DLT. No dose escalations are permitted in any given patient once a dose level has been assigned. While patients experiencing DLT during Cycle 1 may continue on therapy, if toxicity can be managed according to the dose modification guidelines outlined below, the DLT event will contribute to the assessment of MTD for that given cohort. Patients will be considered evaluable for toxicity if they receive any study drug. Patients will be considered evaluable for dose limiting toxicity if they receive at least 75% of both Pomalidomide and MLN9708 and are followed for the full 28 days during cycle 1 or experience a DLT. For the phase II portion, as part of the primary analysis, patients will be considered evaluable for response if they are eligible, have baseline disease assessments, and receive any protocol treatment. As part of a secondary analysis, patients will be considered evaluable for response if they have baseline disease assessments, receive at least 75% of both Pomalidomide and MLN9708 during the first cycle of therapy and have had their disease re-evaluated.

Dose modifications may be performed in all subsequent cycles of treatment regardless of which phase of study the patient is enrolled on. If toxicities cannot be managed by dose modification or the patient cannot tolerate the lowest dose of study drug, the patient is to be discontinued from study treatment. However, patients that have achieved a plateau of response to study

therapy will continue to adhere to the schedule of assessments followed during the treatment phase of the study even though study drug has been discontinued.

## 7.8 Dose Reduction Steps

### 7.8.1 Dose Reduction Steps for Pomalidomide

Pomalidomide Dose Reduction Steps			
Starting Dose	Daily on Days 1 – 21 every 28 days		
4.0 mg	3.0 mg	2.0 mg	1.0 mg
3.0 mg	2.0 mg	1.0 mg	-
2.0 mg	1.0 mg	-	-
1.0 mg	-	-	-

### 7.8.2 Dose Reduction Steps for MLN9708

MLN9708 Dose Reduction Steps			
Starting Dose	Daily on Days 1, 8 and 15 every 28 days		
4.0 mg	3.0 mg	2.3 mg	1.5 mg
3.0 mg	2.3 mg	1.5 mg	-

### 7.8.3 Dose Reduction Steps for Dexamethasone

Dexamethasone Dose Reduction Steps**			
Starting Dose	Days 1, 8, 15 and 22 every 28 days		
40 mg	20 mg	12 mg	
20 mg*	12 mg	6 mg	
12 mg	-	-	

\*: Patients >75 years, at the time of trial registration, will receive a dexamethasone starting dose of 20 mg on the same set schedule.

\*\*: After the patient has been on Dexamethasone over one year, the patient can discontinue Dexamethasone at their next scheduled visit.

- Dexamethasone may be permanently discontinued for toxicity at the discretion of the investigator but the patient can remain on study therapy with pomalidomide and MLN9708 if tolerated.
- After the patient has been on Dexamethasone over one year, the patient can discontinue Dexamethasone at their next scheduled visit.

## 7.9 Dose Modification Guidelines for Treatment Related Toxicity

For recommended concomitant therapy to reduce the risk/severity of potential adverse events refer to Section 7.11. For recommendations on management of adverse events refer to section 7.12. In addition, the table below provides guidelines for dose modification based on toxicity. Dose modifications different from those recommended may be made in consultation with the Lead Principal Investigator based on investigators assessment of toxicity attribution and management of individual patients.

### 7.9.1 Dose Modification for MLN9708 and Pomalidmide During a Cycle of Therapy

Treatment modifications due to MLN9708 and Pomaliomide related AEs during a cycle of therapy are outlined below.

CTCAE Category	AGENTS	Toxicity During a Cycle
Hematologic Toxicity during a cycle of therapy		
≥ Grade 3 neutropenia associated with fever (temperature <math>\geq 38.5^{\circ}\text{C}</math>) or Grade 4 neutropenia	Pomalidomide	Hold dose. Follow CBC weekly. Use of G-CSF is allowed and recommended. If neutropenia resolved to $\leq$ grade 2 within the cycle, resume pomalidomide and continue through the scheduled end of the cycle. If not resolved to $\leq$ grade 2, omit for remainder of cycle and reduce the dose of pomalidomide by one dose level at the start of the next cycle. Omitted doses are not made up. Granulocyte colony stimulating factor [G-CSF], may be used prophylactically on days 21 – 26. Section 7.6.4

	MLN9708	Hold dose. Follow CBC weekly. If neutropenia resolves to $\leq$ grade 2 resume treatment on schedule day of cycle. However, if the Day 8 or 15 dose is held, that dose should be omitted and treatment should continue with next scheduled dose (i.e., if Day 8 is skipped, the next dosing day is Day 15) resume MLN9708 at same dose. If neutropenia dose not resolve to $\leq$ Grade 2 during the cycle and any 2 doses were held due to toxicity then reduce the MLN9708 dose by one level at the start of the next cycle. Granulocyte colony stimulating factor [G-CSF],) may be used prophylactically on days 21 – 26.
Platelet count < 25,000/mm^3 or G3 thrombocytopenia with bleeding	Pomalidomide	Hold dose. Follow CBC weekly. Use of platelet transfusions is allowed to proceed with dosing. If thrombocytopenia resolved to $<$ grade 2 within the cycle, resume pomalidomide and continue through the scheduled end of the cycle. If not resolved to $\leq$ grade 2, omit for remainder of cycle and reduce the dose of pomalidomide by one dose level at the start of the next cycle. Omitted doses are not made up.
	MLN9708	Hold dose. Follow CBC weekly. If thrombocytopenia resolves to $\leq$ grade 2 resume treatment on schedule day of cycle. However, if the Day 8 or 15 dose is held, that dose should be omitted and treatment should continue with next scheduled dose (i.e., if Day 8 is skipped, the next dosing day is Day 15) resume MLN9708 at same dose. If thrombocytopenia dose not resolve to $\leq$ Grade 2 during the cycle and any 2 doses were held due to toxicity then reduce the MLN9708 dose by one level at the start of the next cycle.
For recurrent episodes of hematologic toxicity, MLN9708 and/ or pomalidomide may be dose reduced together or independently at the investigaotrs discretion to manage toxicity.		
Non-Hematologic toxicity during a cycle of therapy		
RASH		Hold pomalidomide and MLN9708. Follow weekly.
Grade 2 or 3	Pomalidomide	Implement supportive therapy (see section 7.11.2)

	MLN9708	If the toxicity resolves to $\leq$ grade 1, restart MLN9708 and pomalidomide and continue through the scheduled end of the cycle. Otherwise, omit for remainder of cycle and reduce the dose of pomalidomide by one dose level at the start of the next cycle. Omitted doses are not made up. For subsequent occurrences, alternate dose reductions with MLN9708 and pomalidomide.
Non-blistering rash Grade 4		Discontinue pomalidomide and MLN9708. Withdraw participant from the study.
Desquamating (blistering) rash-any Grade or Erythema multiforme <math>\geq</math> Grade 3	Pomalidomide/ MLN9708	Discontinue treatment. Withdraw participant from study.
Hyperthyroidism or Hypothyroidism	Pomalidomide	Omit pomalidomide for remainder of cycle, evaluate etiology, and initiate appropriate therapy. Restart pomalidomide at investigator's discretion. For toxicity attributable to pomalidomide, reduce the dose by one dose level.
Neuropathy Grade 2 peripheral neuropathy with pain or Grade 3  Grade 4	Pomalidomide MLN9708	Hold MLN9708. Follow weekly. If the toxicity resolves to $\leq$ grade 1(or baseline), restart MLN9708 at next lower dose level and continue through the scheduled end of the cycle. Otherwise, omit for remainder of cycle and reduce the dose of MLN9708 one dose level at the start of the next cycle. Omitted doses are not made up. For recurrent Grade 2 peripheral neuropathy with pain or grade 3 neuropathy, hold treatment. If the toxicity resolves to $\leq$ grade 1(or baseline), reduce pomalidomide and /or MLN9708 at investigators discretion.  Discontinue treatment. Withdraw participant from study.
Herpes Zoster reactivation any grade	Pomalidomide MLN9708	Hold MLN9708 and pomalidomide until lesions are dry. Initiate antiviral therapy (maintain dose level).
Venous	Pomalidomide/	Hold therapy and start full anticoagulation as

Thrombosis/Embolism <math>\geq</math> Grade 3	MLN9708	appropriate; restart at investigator's discretion (maintain dose level).
Other Pomalidomide or MLN9708 related non-hematologic toxicity Grade <math>\geq</math> 3	Pomalidomide MLN9708	Determine attribution of toxicity and hold both pomalidomide and MLN9708. Follow at least weekly. If toxicity resolves to $\leq$ grade 1 or baseline, resume therapy with one level dose reduction.
Grade 4 related non-hematologic toxicity		Consider permanent discontinuation of therapy. Exceptions may be made following discussion with the Lead Principal Investigator for patients that are experiencing clinical benefit.

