### 4.3 Duration of Study

Accrual, for both phases, is expected to be completed in 26 months; with approximately 2 patients enrolled each month. Patients will be treated in 28-day treatment cycles until disease relapse, progression or unacceptable toxicity, withdrawal of consent, or protocol specified parameters to stop treatment. Patients who discontinue study treatment for reasons other than disease relapse/progression will continue to have disease assessments per International Myeloma Working Group (IMWG) criteria until relapse or progression, initiation of new

anticancer treatment, or death whichever occurs first. Patients will be followed to collect further anticancer treatment and survival information until death, loss to follow-up, withdrawal of consent, study termination or up to 24 months post treatment.

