**City of Hope Data Coordinating Center**

**[contact]**

**COH DCC email: [[contact]](mailto:[contact]) (always use #secure# in subject line)**

Telephone reports must be followed by a written report within 24 hours. Follow-up reports must be submitted in a timely fashion as additional information becomes available.

The Investigator is responsible for notifying the Institutional Review Board (IRB) or Independent Ethics Committee (IEC) in accordance with local institutional regulations, of all SAEs. The Sponsor-Investigator, the City of Hope Data Coordinating Center and/or **Confidential**

Millennium/Celgene may request additional source documentation pertaining to the SAE. If a patient is permanently withdrawn from the study because of a SAE, this information must be included in the initial or follow-up SAE report as well as the Study Discontinuation case report form.

The investigator is responsible for reporting serious adverse events that occur from the signing of the study specific consent through the duration of the post-therapy adverse event collection period to the City of Hope Data Coordinating Center (see section above for submission guidelines), as indicated when using MLN9708 and Pomalidomide within 24 hours of becoming aware of the SAE. Notification can be made via phone or telefacsimile using the MEDWATCH 3500A form. The Sponsor-Investigator, through the COH DCC, will report to Millennium and Celgene within 24 hours.

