#### **All data will be submitted as follows:**

- **Eligibility Checklist:** the participating institutions at the registering site will have completed and faxed this form at the time of registration.
- **On-Study/Baseline Forms:** completed on-study forms are due within two weeks of registration.
- **Treatment Forms (Cycle Forms):** completed forms are due within 2 weeks of completion of a cycle (unless needed sooner for DLT assessment during Phase I). The City of Hope Data Coordinating center will communicate with site staff if forms are needed sooner.

- **Adverse Event Collection:** completed adverse events are due within two weeks of a cycle (unless needed sooner for DLT assessment during Phase I). The City of Hope Data Coordinating center will communicate with site staff if forms are needed sooner.
- **Response/Off Treatment/Off Study/Follow-Up:** forms will be completed each time a patient is evaluated for response, comes off treatment, new follow-up information is obtained or comes off study.

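### Does ordering withdrawal from the study for three severe toxicities cut off the follow-up that Section 4.3 keeps?

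*Combined protocol and SAP*

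**What the plan says.** Section 7.9.1 lists actions by toxicity. In three rows it adds a second step after stopping the drugs:

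- Grade 4 non-blistering rash: "Discontinue pomalidomide and MLN9708. Withdraw participant from the study".
- Desquamating rash of any grade, or erythema multiforme of Grade 3 or higher: "Discontinue treatment. Withdraw participant from study".
- Grade 4 neuropathy: the same words as the row above.

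Section 4.3 covers what happens after treatment. Among the reasons for which treatment ends it names "protocol specified parameters to stop treatment". It then states: "Patients who discontinue study treatment for reasons other than disease relapse/progression will continue to have disease assessments", which run until relapse or progression, new anticancer treatment or death. Separately, it collects "survival information until death, loss to follow-up, withdrawal of consent, study termination or up to 24 months post treatment".

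Section 9.2 gives the investigator the right to withdraw patients from the study. Its reasons are adverse event, lack of adherence, loss to follow-up, progressive disease and study termination. At withdrawal it asks for the End of Treatment procedures and, for an adverse event, follow-up of that event. It neither continues nor ends disease and survival follow-up.

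The second copy of the protocol in the file repeats this text.

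**The concern.** On a plain reading, a patient withdrawn from a study is no longer observed. Section 4.3 has no exception for toxicity, so the two instructions seem to collide for anyone who meets one of the three rows.

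Other wording makes the literal reading plausible. Section 7.7 uses a narrower phrase for toxicity that cannot be managed or where "the patient cannot tolerate the lowest dose of study drug, the patient is to be discontinued from study treatment", so the extra sentence in the three rows could be taken to mean something more. The reporting section provides a study discontinuation form, in a sentence that begins "If a patient is permanently withdrawn from the study because of a SAE". Section 12.6.2 lists leaving treatment and leaving the study as separate occasions: "forms will be completed each time a patient is evaluated for response, comes off treatment, new follow-up information is obtained or comes off study".

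If a site acted on that reading, progression-free survival, duration of response and overall survival would be cut short for a reason tied to toxicity. Censoring of that kind may be informative. Sites might also differ in what they did.

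**Working it through.** The plan states no figure on this point that could be reproduced, so the check sets the passages side by side and then asks what could change.

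**1. Which passage governs follow-up.** Section 7.9 describes its table as guidance on changing doses for toxicity. Section 4.3 is where the duration of treatment and follow-up is set. Its list of treatment-ending reasons already takes in stops required by the protocol, which is what the three rows are. The sentence that follows keeps such patients under disease assessment. Its list of events that end survival follow-up contains death, loss to follow-up, withdrawal of consent, study termination and the 24-month limit. Withdrawal for toxicity is not on that list.

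**2. How the protocol uses the word study.** In the Schedule of Events, following patients for progression and survival appears only in the column for the period after the study. Footnote 11 describes the same contacts as belonging to the end of the study. In this usage a patient leaves the study and enters follow-up.

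**3. Test of the literal reading against Section 9.2.** Progressive disease is a listed reason to withdraw a patient from the study. If withdrawal ended all observation, survival follow-up could be stopped at progression for any patient. That cannot be squared with Section 4.3, which collects survival and later treatment with no exclusion of progressed patients. Read literally, the phrase would undermine the overall survival endpoint itself. Read as leaving the treatment phase, it leaves Sections 4.3, 7.9.1, 9.2 and the schedule consistent.

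**4. Other duties.** New primary malignancies must be reported for at least three years after the last dose under Section 11.3, and for at least two years from the first MLN9708 dose under the list of events of special interest. Neither duty is lifted for a withdrawn patient, which again favours the mild reading.

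**5. What could change under the literal reading.**

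- Primary denominator: Section 10.1.2 counts eligible patients with a baseline assessment who received any protocol treatment. An affected patient stays in.
- Primary numerator: a response awaiting confirmation could be affected. However, Section 9.2 requires the End of Treatment procedures, footnote 10 requires myeloma laboratory tests there if the last were more than three weeks old, and Appendix 15.4 accepts two consecutive assessments at any time before new therapy.
- Secondary endpoints: footnote 11 plans a contact every 3 months for 2 years, so 24 / 3 = 8 contacts per affected patient at most.
- Frequency: the documents give no rate for the three triggers combined. In C16004 neuropathy was limited to Grade 1 or 2, so no Grade 4 case occurred among 52 patients. The one-sided 95% upper bound is 1 − 0.05^(1/52) = 5.6%. That covers one trigger, with MLN9708 alone. Grade 4 rash is not separated from Grade 3 in the background tables. A numerical bias therefore cannot be derived.

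**The case for a change.** The best case for acting is that the drafters seem to vary their wording on purpose. In the same table, other Grade 4 related non-hematologic toxicity leads only to considering permanent discontinuation of therapy, and Section 7.10 also speaks only of stopping treatment. Three rows go further, and the forms distinguish the two states. Section 9.2 does not resolve it: its list mixes events that do end follow-up, such as loss to follow-up, with one that does not end survival follow-up, progressive disease. Section 10.1.4 names Kaplan-Meier estimation but gives no censoring rule. With several sites, one clarifying sentence would cost almost nothing.

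Part of this stands. The term is undefined, and the looseness sits in Section 9.2 at least as much as in the three rows. The rest is weaker. A difference in phrasing between 7.7 and 7.9.1 does not create an instruction to stop observing a patient. The existence of a discontinuation form says nothing about survival follow-up. The list in 12.6.2 never equates leaving the study with withdrawal under 7.9.1, and it also provides for new follow-up information. That a clarification is cheap does not show that the plan is wrong without it.

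**Conclusion.** The concern does not call for a change. It identifies an undefined term that can be read in two ways. The harmless reading is the one that fits Section 4.3, Section 9.2, the schedule and the malignancy reporting duties together. A data centre and analyst following Section 4.3 would keep these patients under observation unless they withdrew consent, were lost to follow-up or the study closed, and would censor accordingly.

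No sample size, stopping boundary, analysis population or primary conclusion moves. The most that could be lost is eight quarterly contacts for each patient at a site that chose the literal reading, affecting mainly descriptive time-to-event estimates. This rests on two assumptions: that sites treat Section 4.3 as governing follow-up, and that the three triggers are uncommon, which the background data suggest for neuropathy but cannot establish for rash. No view is taken on the treatment-stopping criteria themselves.
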